## **9.4 DATA SOURCES**

The data source for this meta-analysis is the study databases for 1245.25, 1245.110, and 1245.121. All 3 studies are large, long-term, randomised, placebo-controlled, double-blind, parallel-group, and event-driven. Data from individual patients from the 3 studies, not the result estimates of the studies, will be pooled in the meta-analysis. See [Section 9.1](#) for more details.

## **9.5 STUDY SIZE**

This meta-analysis will be based on patients treated with at least 1 dose of study medication (“treated set”) in the 3 studies. Patients are assigned to treatment groups according to randomisation.

Study 1245.25 included 7020 patients treated with empagliflozin 10 mg (N = 2345), empagliflozin 25 mg (N = 2342), or placebo (N = 2333).

Study 1245.110 will randomise approx. 4126 patients to empagliflozin 10 mg or placebo in a 1:1 ratio. Study 1245.121 will randomise approx. 2850 patients to empagliflozin 10 mg or placebo in a 1:1 ratio. Almost all randomised patients are expected to be treated.

## **9.6 DATA MANAGEMENT**

The study databases for 1245.25, 1245.110, and 1245.121 will be used. The data is collected and managed according to the respective clinical trial protocols. SAS data sets from

individual trials will be combined for the meta-analysis based on individual patient data. All statistical analyses will be implemented using the statistical software SAS® 9.4 or higher.

## **9.7 DATA ANALYSIS**

This meta-analysis will be exploratory. For the primary outcome of LLA events and for the secondary outcome of AEs related to amputation, a Cox proportional hazards regression model for modelling the time to first event will be used, including the factors study, diabetes mellitus status (T1DM, T2DM, no diabetes), and treatment (all empa vs. placebo). Study is assumed as fixed effect in this meta-analysis. For treatment comparison, hazard ratios with corresponding 95% CIs as well as corresponding p-values will be presented (see the SAP [[c16853237](#), Section 4.3]).

All analyses will be based on the treated set, which includes all patients treated with at least 1 dose of study medication (as randomised). Due to the different patient eligibility criteria (see [Section 9.2.2](#)) and methods in capturing LLA and related events (see [Section 9.3.2.1](#)), two analysis groupings will be used in the meta-analysis. SAF-M1 includes all 3 studies while SAF-M2 includes studies 1245.110 and 1245.121 (Table 9.7: 1; also see the SAP [[c16853237](#), Table 3.1.2: 1]). All analyses will be carried out separately for each SAF and for each study, unless otherwise indicated in [Table 9.7: 2](#).

Table 9.7: 1 Overview of analysis groupings and individual studies

Grouping	Description	Studies	Purpose
SAF-M1	All studies	1245.25	Frequencies, incidence rates and time to onset of amputation events
		1245.110 1245.121	Frequencies, incidence rates and time to onset for related events based on selected adverse events
SAF-M2	Chronic heart failure studies	1245.110	Frequencies, incidence rates and time to onset of amputation events
		1245.121	Frequencies, incidence rates and time to onset for related events based on selected adverse events
			Details on lower limb amputations

The results of the meta-analysis will be presented mainly in tabular form, and when appropriate, in graphical form.

Tabulations of frequencies for categorical data will include all different categories and display the number of observations and the percentage (%) in a category relative to the respective treatment group (placebo, empa 10 mg, 25 mg, all empa). The category "missing" will be displayed if there are actually missing values. Percentages will be based on all patients in the respective patient set whether they have non-missing values or not.

Proprietary confidential information © 2019 Boehringer Ingelheim International GmbH or one or more of its affiliated companies

For continuous variables the set of summary statistics in tables is: N (number of patients with non-missing values) / Mean / SD / Min / Q1 (lower quartile) / Median / Q3 (upper quartile) / Max.

For frequency analyses based on pooled data the estimates for the relative frequency is defined as follows:

$$\hat{p}_j = \frac{\sum_{i=1}^k w_{ji} \cdot \hat{p}_{ji}}{\sum_{i=1}^k w_{ji}}, \text{ where}$$

$\hat{p}_{ji}$  relative frequency in treatment group j and study (i=1,.., k)

$w_{ji} = \frac{n_{ji}}{\sum_i n_{ji}}$  denotes the weight of study i,  $i=1, \dots, k$  in treatment group j

$n_{ji}$  number of patients in treatment group j and study i (i=1, ..k)

The frequency (%) of AEs does not take into account the duration of treatment. This is particularly important when studies with different treatment durations are pooled for analysis. In this case incidence rates may provide more accurate comparisons among groups.

Incidence rate is the number of new cases of an event occurring in a specified time period divided by the cumulative time at risk (see [Section 9.3.1](#) for the derivation).

The incidence rate per 100 patient-years is calculated as follows:

Incidence rate [1/100 pt-yrs] = 100 \* number of patients with event / sum of time at risk over all patients [years].

The estimate for a pooled incidence rate in treatment group j is defined as follows:

$$\hat{IR}_j = \frac{\sum_{i=1}^k w_{ji} \cdot \hat{IR}_{ji}}{\sum_{i=1}^k w_{ji}}, \text{ where}$$

$\hat{IR}_{ji}$  Incidence rate in treatment group j and study (i=1,.., k)

$w_{ji} = \frac{t_{ji}}{\sum_i t_{ji}}$  denotes the weight of study i,  $i=1, \dots, k$  in treatment group j

$w_{ji} = \frac{t_{ji}}{\sum_i t_{ji}}$  denotes the weight of study  $i$ ,  $i=1, \dots, k$  in treatment group  $j$

$t_{ji}$  sum of time at risk in treatment group  $j$  and study  $i$  ( $i=1, \dots, k$ )

Due to the different study designs, not all analyses will be performed for each of the 2 pools. Table 9.7: 2 indicates which safety analyses will be performed for which pool and the individual studies (also see the SAP [[c16853237](#), Table 4.3: 1]).

Table 9.7: 2 Overview of analyses that will be performed for the different study poolings and for the individual study

Endpoint	Poolings and individual study				
	SAF-M1	SAF-M2	Study 1245.25	Study 1245.110	Study 1245.121
Disposition, demographics, exposure	Yes	Yes	Yes	Yes	Yes
Concomitant diagnoses and therapies	Yes	Yes	Yes	Yes	Yes
Lower limb amputation					
Frequencies	Yes	Yes	Yes	Yes	Yes
Incidence rates	Yes	Yes	Yes	Yes	Yes
Time to onset analyses	Yes	Yes	Yes	Yes	Yes
Time to onset analyses with competing risk	Yes	-	-	-	-
Sensitivity analyses (heterogeneity analyses, forest plot)	Yes	Yes	-	-	-
Adverse events related to amputations (definition based on list of PTs)					
All patients					
Frequencies	Yes	Yes	Yes	Yes	Yes
Incidence rates	Yes	Yes	Yes	Yes	Yes
Time to onset analyses	Yes	Yes	Yes	Yes	Yes
Patients with amputations only, i.e. preceding events					
Frequencies	Yes	Yes	Yes	Yes	Yes
Incidence rates	Yes	Yes	Yes	Yes	Yes
Time to onset analyses (KM only)	Yes	Yes	Yes	Yes	Yes
Lower limb amputation events occurring after the first LLA event					
Descriptive Statistics (Frequency tables with absolute and relative frequencies)	Yes	Yes	Yes	Yes	Yes
Adverse Events related to amputations occurring after the first LLA event					
Descriptive Statistics (Frequency tables with absolute and relative frequencies)	Yes	Yes	Yes	Yes	Yes

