\widehat{IR}_{ji} Incidence rate in treatment group j and study ($i=1, \dots, k$)

$$w_{ji} = \frac{t_{ji}}{\sum_i t_{ji}}$$

denotes the weight of study i , $i=1, \dots, k$ in treatment group j

$w_{ji} = \frac{t_{ji}}{\sum_i t_{ji}}$ denotes the weight of study i , $i=1, \dots, k$ in treatment group j

t_{ji} sum of time at risk in treatment group j and study i ($i=1, \dots, k$)

The incidence rates will be calculated with two types of time at risk calculations.

The main analysis is the on-treatment approach where patients are censored at the date of treatment stop + 7 days and the secondary analysis is the ITT analysis where patients are censored at the last day of follow-up if no event occurred.

Time to event analyses

Kaplan Meier (KM) methods of cumulative incidence functions will be performed for time to event data (time to first event).

For pooled data across studies the cumulative incidence functions will be shown overall and stratified by study. The main analysis will be performed with censoring at the date of last study medication intake + 7 days for patients without event. An additional analysis will be performed whereby patients with no events will be censored at the date of last follow-up.

Cox proportional hazards models for modelling time to first event will be applied using factors study, DM status (T1DM, T2DM, no diabetes) and treatment (all empa vs placebo). For treatment comparison, hazard ratios with corresponding 95% confidence intervals as well as corresponding p-values will be presented.

The proportional hazards assumption will be explored by plotting $\log(-\log(\text{survival function}))$ against the log of time by treatment group and checked for parallelism. The interaction of treatment with log of time will be included in the model described above for an exploratory analysis. Further, Schoenfeld residuals for each covariate and treatment will be plotted against time and $\log(\text{time})$.

Competing risk analyses for time to event endpoints

Death is a competing risk for lower limb amputations. A competing risk analysis using a regression model by Fine and Gray (1999) [1] for amputations considering death as a competing event will therefore be performed. The regression model will include the following co-variables: study, diabetes mellitus (T1DM, T2DM, no diabetes), and treatment (empa vs. placebo).

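### In the three-study pool (SAF-M1), the pooled frequencies and incidence rates weight studies differently in each arm, so unequal allocation across studies can create a treatment difference where none exists

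*Protocol*

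**What the plan says.** Protocol 9.7 defines the pooled relative frequency in treatment group j as a weighted mean of the study frequencies. The weight is n_ji divided by the sum of n_ji over studies, where n_ji is the "number of patients in treatment group j and study i (i=1, ..k"). SAP 4.3 repeats the formula. The pooled incidence rate has the same form, with t_ji in place of n_ji, the "sum of time at risk in treatment group j and study i".

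Percentages are tabulated "relative to the respective treatment group (placebo, empa 10 mg, 25 mg, all empa"). On pooling studies of different duration, Protocol 9.7 says of rates: "In this case incidence rates may provide more accurate comparisons among groups". SAP 4.3 adds, for Kaplan-Meier displays: "For pooled data across studies the cumulative incidence functions will be shown overall and stratified by study".

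Protocol Section 8 names frequencies and incidence rates in the primary objective next to hazard ratios. Protocol 9.7.1 lists them among the methods for comparing empagliflozin with placebo in SAF-M1. The Cox model includes study as a fixed factor. No study-adjusted version of the pooled frequencies or rates is planned, and the limitations in Protocol 9.9 do not mention the unequal allocation.

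**The concern.** The formulas look like a study-weighted average but make no adjustment for study, because each arm carries its own weights. That would be harmless if every study used the same allocation ratio. Here 1245.25 has two active arms and one placebo arm, and the heart-failure studies have one of each. Treatment is therefore associated with study in SAF-M1 by design.

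Amputation risk need not be equal across the studies. Study 1245.25 enrolled only patients with type 2 diabetes and high cardiovascular risk, whereas the heart-failure studies also take patients without diabetes. Amputations in 1245.25 were found by retrospective search, and in the other two on dedicated eCRF pages. Protocol 9.9 itself expects heterogeneity and possibly different completeness of reporting.

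Any such difference passes straight into the comparison of the pooled columns. The result could be a spurious excess, a spurious protective effect, or an apparent dose gradient, in a safety study that a regulator requested because of an amputation signal. The same formulas feed the SAF-M1 subgroup tables (Protocol 9.7.2.3) and the pooled row of the forest plots (Protocol 9.9). That row could show an arm difference that appears in none of the studies plotted beside it.

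**Working it through.** **Inputs.** Protocol 9.5 gives 1245.25 as "empagliflozin 10 mg (N = 2345), empagliflozin 25 mg (N = 2342), or placebo (N = 2333"). It also says "Study 1245.110 will randomise approx. 4126 patients to empagliflozin 10 mg or placebo in a 1:1 ratio", and plans 2850 patients at 1:1 in 1245.121. The totals reproduce: 2345 + 2342 + 2333 = 7020, and 7020 + 4126 + 2850 = 13,996, against the approx. 14 000 in Protocol 9.1. Heart-failure counts below are planned randomised numbers split 1:1, that is (4126 + 2850)/2 = 3488 per arm.

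**Step 1: the weights cancel.** They sum to 1 within each arm. With x_ji patients with events and N_j = Σ_i n_ji:

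Σ_i (n_ji/N_j)(x_ji/n_ji) = Σ_i x_ji / N_j.

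With T_j = Σ_i t_ji, the rate likewise becomes Σ_i x_ji / T_j. Both are crude pooling.

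**Step 2: share of 1245.25 in each pooled column.**

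- All empagliflozin: 4687/(4687 + 3488) = 4687/8175 = 57.3%
- Placebo: 2333/(2333 + 3488) = 2333/5821 = 40.1%
- 10 mg: 2345/(2345 + 3488) = 2345/5833 = 40.2%
- 25 mg: 100%

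**Step 3: apparent ratios when treatment has no effect in any study.** Let r be the amputation risk in the heart-failure studies divided by that in 1245.25. The documents do not give r, so a range is shown.

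- All empa/placebo = (0.5733 + 0.4267r)/(0.4008 + 0.5992r)
- 25 mg/placebo = 1/(0.4008 + 0.5992r)

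| r (assumed) | All empa/placebo | 25 mg/placebo | 10 mg/placebo |
|---|---|---|---|
| 0.25 | 1.235 | 1.82 | 1.002 |
| 0.5 | 1.123 | 1.43 | 1.001 |
| 0.75 | 1.051 | 1.18 | 1.000 |
| 1 | 1.000 | 1.00 | 1.000 |
| 2 | 0.892 | 0.63 | 0.999 |

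For example, with 2% in 1245.25 and 1% in heart failure in every arm, the pooled table shows 0.5733 × 2% + 0.4267 × 1% = 1.573% on empagliflozin and 0.4008 × 2% + 0.5992 × 1% = 1.401% on placebo.

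**Step 4: incidence rates.** Protocol 9.1 gives a median exposure of 2.6 years in 1245.25 and up to 3 years expected in the heart-failure studies. Take 2.6 years per patient in 1245.25 and, as an assumption, 1.5 years in heart failure. The time share of 1245.25 is 12,186.2/17,418.2 = 70.0% on empagliflozin and 6,065.8/11,297.8 = 53.7% on placebo. With r now a ratio of rates, the null ratio is 1.19 at r = 0.25, 1.11 at r = 0.5 and 0.89 at r = 2. With 3 years assumed in heart failure it is 1.24, 1.13 and 0.90. Using person-time does not remove the problem.

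**Step 5: when there is a true effect.** A true ratio of 0.85 in every study shows as 0.85 × 1.235 = 1.05 at r = 0.25. A true 0.80 shows as 0.90 at r = 0.5 and 0.71 at r = 2.

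**Step 6: the remedy, checked.** Common weights by planned size are 7020/13,996 = 50.2%, 4126/13,996 = 29.5% and 2850/13,996 = 20.4%. With these, or with Mantel-Haenszel weights, the all-empagliflozin/placebo ratio returned the true within-study value (1.00, 0.80 or 1.30) for r = 0.25, 0.5, 2 and 4.

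**SAF-M2.** Both arms have weights 2063/3488 = 59.1% and 1425/3488 = 40.9%, so the planned numbers give no distortion.

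**The case against.** The strongest reply is that the effect measure is already protected. The Cox and Fine-Gray models include study, and SAP 4.3 ties the treatment comparison to hazard ratios. No ratio, interval or test is planned on the pooled frequencies or rates. Per-study tables, within-study forest plots, study-stratified Kaplan-Meier curves and the balanced SAF-M2 all give unconfounded contrasts. The 1245.25 tables already set 25 mg against its own placebo, no formal dose comparison is planned, and the pooled 10 mg column is practically undistorted against placebo. The size and direction rest on an assumed r, and the bias vanishes at r = 1. The remark about more accurate comparisons concerns treatment duration, not study adjustment. Common weights also need care in subgroups to which a study contributes no patients.

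Each of these points is fair and narrows the problem to the SAF-M1 all-empagliflozin and 25 mg summaries and the overall curve. None corrects those summaries. They answer a primary objective, are listed as a means of comparing the arms, and will be read side by side. An adjusted hazard ratio does not repair an unadjusted table; it leaves room for the two to conflict. The subgroup difficulty is met by computing weights within each subgroup, where an absent study gets weight zero.

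**Conclusion.** The concern holds. The SAF-M1 pooled frequencies, incidence rates and overall Kaplan-Meier curve confound treatment with study. The algebra and the shares (57.3%, 40.1% and 100%) follow from the documents, using planned numbers for the heart-failure studies. The size of the distortion depends on the unknown risk ratio between studies. Over assumed values from 0.25 to 2, a true null would appear in the frequencies as 1.24 down to 0.89 for all-empagliflozin against placebo, and as 1.82 down to 0.63 for 25 mg against pooled placebo. There is no distortion if study risks are equal. The hazard ratios, the per-study results, SAF-M2 and the pooled 10 mg contrast are not materially affected. The plan should be changed before the heart-failure databases lock, so that the choice of weights is not made after seeing results.

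**What to change.** In Protocol 9.7 and SAP 4.3, replace the arm-specific weights with one weight per study, common to all arms:

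- Frequencies: w_i = Σ_j n_ji / Σ_i Σ_j n_ji
- Rates: w_i = Σ_j t_ji / Σ_i Σ_j t_ji

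Here j runs over placebo and all-empagliflozin, so that no patient is counted twice. Mantel-Haenszel weights by study are an acceptable alternative. Apply the change to the SAF-M1 main tables, the subgroup tables (with weights recomputed within each subgroup) and the pooled row of the forest plots. Show the 25 mg column only within 1245.25, against that study's placebo. Replace the overall SAF-M1 Kaplan-Meier curve with study-specific curves or a study-weighted average of them. Add the unequal allocation to the limitations in Protocol 9.9.

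The cost is two formula lines in each document, some edits to table and figure specifications, and minor SAS code. The adjusted percentage will no longer equal n/N, so both should be shown, with the crude one labelled as unadjusted for study.

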### **9.7.1 Main analysis**

LLA events (primary outcome) and AEs related to amputation (secondary outcome) will be analysed using frequency analyses, incidence rates, Kaplan-Meier estimates, and Cox proportional hazards models to compare empagliflozin with placebo in the pooled populations of SAF-M1, SAF-M2, and for each of the 3 studies (1245.25, 1245.110, and 1245.121) separately. Kaplan-Meier analyses (cumulative incidence functions) for time to first event will be provided by treatment and stratified by study.

Cox proportional hazards models will include the factors study, diabetes mellitus status (T1DM, T2DM, no diabetes), and treatment (all empa vs placebo).

As the primary analysis, the “on-treatment” approach will include events with an onset date within the treatment period (from first to last dose of study medication plus 7 days to account for the residual drug effect).

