**1245.110 (EMPEROR-Preserved) and 1245.121 (EMPEROR-Reduced), both ongoing**

**Aim:** To investigate the safety and efficacy of empagliflozin versus placebo on top of guideline-directed medical therapy in patients with heart failure with reduced or preserved ejection fraction

**Population:** T2D and non-T2D, age ≥18 years, chronic HF (NYHA II–IV)

Figure 9.1: 1 Design of studies 1245.25, 1245.110, and 1245.121

QD/qd, once daily; T2DM, type 2 diabetes mellitus; LVEF, left ventricular ejection fraction; SoC, standard of care

\* Guideline-directed therapies

This meta-analysis will be exploratory. All analyses will be based on the treated set, which includes all patients treated with at least 1 dose of study medication (as randomised). Due to the different patient eligibility criteria (see [Section 9.2.2](#)) and methods in capturing LLA and related events (see [Section 9.3.2.1](#)), two analysis groupings will be used in the meta-analysis. SAF-M1 includes all 3 studies while SAF-M2 includes studies 1245.110 and 1245.121. All

analyses will be carried out separately for each SAF and for each study, unless otherwise indicated in [Section 9.7.1](#) and [9.7.2](#).

The primary outcomes are LLA events (see [Section 9.3.2.1](#)).

LLA events will be analysed using frequency analyses, incidence rates, Kaplan-Meier estimates, and Cox proportional hazards models to compare empagliflozin with placebo. For SAF-M2, where additional information on LLA events are collected on the eCRF, the reasons leading to LLA, the number of LLA episodes, level of LLA, etc., will be summarised.

As the primary analysis, the “on-treatment” approach will include events with an onset date within the treatment period (from first to last dose of study medication plus 7 days to account for the residual drug effect). An ITT approach will be used as a secondary analysis, which includes all events during the observation period after starting randomised treatment, regardless if the patient was taking study medication or not when the event occurred.

Since deaths are competing events to amputations, a competing risk analysis considering all-cause death and a cumulative incidence analysis will be carried out.

Subgroups by demographics, baseline medical conditions, and baseline therapies will be analysed for LLA events for SAF-M1 and SAF-M2 (see [Section 9.3.3](#) for subgroup variables).

The secondary outcomes are AEs related to amputation (see [Section 9.3.2.2](#)).

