4.3.2.2.1 Lower limb amputation

Frequency tables of patients with LLA (see [Section 4.1.1.1](#)) by treatment, SOC and PT will be provided. In addition incidence rates will be displayed.

Kaplan Meier analyses (cumulative incidence functions) for time to first LLA will be provided by treatment and stratified by study if feasible. Cumulative proportion of patients and the number of patients "at risk" will be provided.

The number of LLA episodes per patients will be summarized in a frequency table. Additionally a listing of patients with recurrent events will be provided.

For SAF-M2 the following analyses will be performed additionally:

- Frequencies of reasons leading to the LLA
- Number of LLA episodes per patient
- Number of LLA episodes per patient excluding those due to trauma and tumor
- Level of amputation for the first LLA, excluding amputation due to trauma and tumor (highest)
- Number of patients having a major LLA as first LLA
- Number of patients with any major LLA
- Number of patients having a knee or above knee LLA as first LLA
- Number of patients with any knee or above knee LLA

Descriptive statistics will be provided to summarize all amputation events occurring after the first LLA event.

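### Kaplan-Meier curves for lower-limb amputation that censor deaths are called cumulative incidence functions, and the display that accounts for death is planned only for SAF-M1

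*Protocol*

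**What the plan says.** **Label.** Protocol Section 9.7.1 states that "Kaplan-Meier analyses (cumulative incidence functions) for time to first event will be provided by treatment and stratified by study". SAP Section 4.3.2.2.1 repeats this for the primary outcome: "Kaplan Meier analyses (cumulative incidence functions) for time to first LLA will be provided by treatment and stratified by study if feasible". It then promises "Cumulative proportion of patients and the number of patients" at risk. The general time-to-event text in SAP Section 4.3 equates the two terms in the same way.

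**Censoring.** SAP Section 4.3 gives one rule for these curves. Patients without an event are censored at last intake plus 7 days in the main analysis, and at last follow-up in the additional one. Death is not treated separately.

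**Competing risk.** The same SAP section states: "Death is a competing risk for lower limb amputations". It plans a Fine-Gray model and a cumulative-incidence graph of amputation and death, both on-treatment and to last follow-up. Protocol Sections 9.1 and 9.7.2.1 also name death as a competing event.

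**Scope.** In Protocol Table 9.7: 2 and SAP Table 4.3: 1, the row "Time to onset analyses with competing risk" is marked Yes for SAF-M1 and has a dash for SAF-M2, 1245.25, 1245.110 and 1245.121. Ordinary time-to-onset analyses of LLA are marked Yes in all five columns. The only reason offered is general: "Due to the different study designs, not all analyses will be performed for each of the 2 pools".

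**The concern.** When death competes with amputation, 1-KM with deaths censored does not estimate the proportion of patients who have an amputation. It describes what would happen if nobody died first, assuming that the patients who died would have had the same LLA hazard as those who remained. It is a legitimate display under its own name, but the plan names it as cumulative incidence and as a proportion of patients.

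Two consequences follow. In SAF-M1 the report would show two different LLA curves under the same name. In SAF-M2, the pool where LLA is captured prospectively on dedicated eCRF pages, and in each single study, the overstated curve would be the only one.

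What is at stake is the reading of absolute-risk curves. The objectives in Protocol Section 8 (frequencies, incidence rates, hazard ratios) do not depend on them.

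**Working it through.** **1. Are deaths censored?** No sentence says so. It follows from the SAP rule, which censors every patient without an LLA and makes no exception. A patient who dies without an LLA is therefore censored at last intake plus 7 days or at last follow-up.

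**2. Does any other row of the tables cover the missing display?** No. The row does not name the graph, but the SAP places the graph under its competing-risk heading, and that row is limited to SAF-M1.

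**3. Which text sets the scope?** Protocol Section 9.1 says that all "analyses will be carried out separately for each SAF and for each study, unless otherwise indicated in" Sections 9.7.1 and 9.7.2. Neither section restricts the competing-risk analysis. Section 9.7 instead refers to Table 9.7: 2 for exceptions, and the restriction is there. The table governs, so the scope is clear, but the pointer in Section 9.1 is wrong.

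**4. How large is the overstatement?** The plan has no figure to reproduce and gives no LLA or death rates. Inputs:

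- LLA rate h: 0.003 and 0.006 per year (assumed)
- Death rate d: 0.03 to 0.12 per year (assumed)
- Time T: 2 and 3 years. Protocol Section 9.1 expects exposure of up to 3 years in the two heart failure studies.

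With constant hazards:

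- 1-KM = 1 - exp(-hT)
- Cumulative incidence (CIF) = h/(h+d) × [1 - exp(-(h+d)T)]

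Example with h = 0.006, d = 0.10, T = 3:

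- 1-KM = 1 - exp(-0.018) = 1.78%
- CIF = (0.006/0.106) × [1 - exp(-0.318)] = 1.54%
- Ratio 1.157, excess 0.24 points

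At T = 2 the same rates give 1.19% against 1.08%.

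| T (years) | Deaths per 100 pt-yrs | 1-KM / CIF | Excess in points, LLA 0.3 per 100 pt-yrs | Excess in points, LLA 0.6 per 100 pt-yrs |
|---|---|---|---|---|
| 2 | 3 | 1.030 | 0.018 | 0.035 |
| 2 | 5 | 1.051 | 0.029 | 0.058 |
| 2 | 10 | 1.103 | 0.056 | 0.111 |
| 2 | 12 | 1.125 | 0.066 | 0.132 |
| 3 | 3 | 1.046 | 0.039 | 0.078 |
| 3 | 5 | 1.077 | 0.064 | 0.127 |
| 3 | 10 | 1.157 | 0.122 | 0.242 |
| 3 | 12 | 1.190 | 0.143 | 0.285 |

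**5. Does uneven follow-up change this?** A simulation of 6 million patients used administrative follow-up uniform on 1-3 years and discontinuation at 0.10 per year. With h = 0.006 and d = 0.10 it gave 1.184% (1-KM) against 1.074% (Aalen-Johansen) at 2 years, ratio 1.103. This equals the closed form.

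**6. What if fewer deaths fall on treatment?** If only half of the deaths in the example fall within last dose plus 7 days, d is 0.05. The excess is then 7.7% (0.13 points) at 3 years and 5.1% (0.06 points) at 2 years.

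**7. How does this compare with sampling error?** SAF-M2 has about (4126 + 2850)/2 = 3488 patients per arm. The 95% half-width is 1.96 × sqrt(p(1-p)/3488), with p the CIF. This gives 0.24-0.36 points at 2 years and 0.29-0.43 at 3 years if all patients are followed to T, and more otherwise. The excess is smaller than this throughout the grid.

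**8. What does the added display bring with it?** Take equal LLA hazards in both arms (h = 0.006), d = 0.03-0.12 on placebo, and an assumed death hazard ratio of 0.7-0.9. The CIF ratio is then 1.003-1.035 at 2 years and 1.004-1.052 at 3 years, while the 1-KM ratio stays at 1.00.

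**The case against.** The plan already deals with competing risk. It has a Fine-Gray model and a proper cumulative-incidence graph in the pool of all three studies, under both censoring schemes. Limiting a supplementary analysis to the full pool is a pre-specified choice on which both tables agree. Wherever the label appears the method is named as Kaplan-Meier, so an attentive reader can tell which estimator is plotted. The excess rests on assumed rates and is below sampling error. In the on-treatment analysis, stopping treatment is censored too, so even an Aalen-Johansen curve is not an observed proportion of patients. The added curves can also shift through mortality alone.

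Much of this stands, and it is why the point is minor. It does not remove the point. Naming Kaplan-Meier does not make the bracketed label or the reference to a proportion of patients correct. The overstatement always runs in the same direction, whereas sampling error does not. Differing study designs do not explain the dashes, because SAF-M1 pools patient-level data from these same three studies and the data are therefore available. The shift through mortality is a reason to show both curves with clear labels and to keep the Cox hazard ratio as the main contrast. The cross-reference is only a pointer to correct; it does not create a contradiction in scope.

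**Conclusion.** The concern holds and is minor. As written, the LLA Kaplan-Meier curves overstate what their label says they show, and SAF-M2 and the three single studies have no curve that accounts for death. Over the assumed rates the overstatement is 3.0-12.5% relative at 2 years and 4.6-19% at 3 years, at most 0.29 percentage points. It grows with the death rate and shrinks if fewer deaths fall in the on-treatment window.

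These sizes rest on constant hazards and on LLA and death rates that the documents do not give. The direction does not depend on the particular rates: the excess is positive whenever deaths occur before an LLA. LLA frequencies, incidence rates and the cause-specific Cox hazard ratio are not affected.

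**What to change.** 1. In Protocol Section 9.7.1 and SAP Sections 4.3 and 4.3.2.2.1, label the LLA curves as 1-KM with deaths censored, and stop describing them as cumulative incidence or as a proportion of patients. For consistency, check the similar wording for related AEs in Protocol Section 9.7.2.1 and SAP Section 4.3.2.2.2.
2. In Protocol Table 9.7: 2 and SAP Table 4.3: 1, mark the competing-risk row Yes for SAF-M2 and the three studies, at least for the Aalen-Johansen display of amputation and death by treatment. Show it beside the Kaplan-Meier curves, on-treatment and to last follow-up. Further Fine-Gray regressions are optional.
3. Make Protocol Section 9.1 refer to Table 9.7: 2 for exceptions, as Section 9.7 does.
4. Keep the cause-specific Cox hazard ratio as the main contrast. Add a note that a treatment effect on mortality can by itself move the cumulative-incidence ratio, and that the on-treatment curve covers events only up to last dose plus 7 days.

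The cost is small: some relabelling, one row in each of two tables, one cross-reference, one note and about eight figures (four data sets, two censoring schemes each). No new data are needed.
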